2.2 Objectives of the study

2.2.1 Primary objective

The primary objective is to describe the characteristics of mRCC patients achieving a CR with Sunitinib (Cases) and compare them to the characteristics of mRCC patients not achieving a CR with Sunitinib (Controls) to identify factors associated with the occurrence of CR.

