3.2.2. Patient population

40 patients with metastatic renal cell carcinoma in CR with Sunitinib (**Cases**) and 80 patients with metastatic renal cell carcinoma receiving first-line treatment with Sunitinib (**Controls**) will be included in this research and followed for a period of 36 months.

Inclusion and exclusion criteria for Cases

Inclusion criteria

- Adult patients (≥ 18 years)
- Patients with mRCC confirmed by histological analysis
- Treated with Sunitinib according to a regimen in the section of the Summary of Product Characteristics (SmPC)
- Presenting a complete remission in the preceding 5 years (according to RECIST v1.1) with Sunitinib only or combined with localized treatment (surgery, radiotherapy, cryoablation or radiofrequency ablation)
- Patients of childbearing age using a mandatory method of contraception
- Affiliated to a social security scheme
- Informed about the study methods and having given their consent

Exclusion criteria

- Complete remission occurring in the absence of treatment with Sunitinib

Inclusion and exclusion criteria for Controls

Inclusion criteria

- Adult patients (≥ 18 years)
- Life expectancy ≥ 3 months
- Patients with mRCC confirmed by histological analysis
- No previous treatment with Sunitinib
- Patients for whom the indication of Sutent® is retained in compliance with the text in the SmPC
- Platelets $\geq 100 \times 10^9/l$, hemoglobin $> 9 \text{ g/dl}$, neutrophils $> 1.5 \times 10^9/l$
- Bilirubin $< 2 \text{ mg/dl}$, aspartate transaminase (AST) and alanine transaminase (ALT) ≥ 2.5 times upper limit of normal or ≤ 5 times upper limit of normal in the presence of hepatic metastases
- Patients of childbearing age using a mandatory method of contraception
- Affiliated to a social security scheme
- Informed about the study methods and having given their consent

Exclusion criteria

- Previous systemic treatment
- Patients who are pregnant or breastfeeding
- Any contraindications to Sunitinib in accordance with the text in the SmPC

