8.1.1. Type of study

It is a cross-sectional then longitudinal, comparative, multicenter, prospective, case-control observational study with collection of blood samples.

In addition to the patient's usual medical treatment, as described in the HAS's long-term diseases guide, validated by a multidisciplinary working group ¹⁹, the specific monitoring methods provided for in this research comprise of:

- Blood sampling of 2 times 5 ml into 2 EDTA tubes done at screening visit during CR and during disease progression, if it occurs, in the 40 patients with metastatic renal cell carcinoma in CR with Sunitinib (**Cases**).
- Blood sampling of 2 times 5 ml into 2 EDTA tubes done before starting Sunitinib, at 6 months, at 12 months and during disease progression, in 80 patients with metastatic renal cell carcinoma without CR with Sunitinib throughout the 36 months of the study (**Controls**).

Therefore, these monitoring methods only involve negligible risks and constraints.

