8.1.3. Obtaining of patient's informed consent

An informed consent form, accompanied by a patient information leaflet in which the purpose of the blood samples collected will be clearly stated, will be signed by each patient before any data collection.

In addition, it will be mentioned that the histological samples taken at the diagnosis of the patients will be collected in order to constitute a bank of samples

A second informed consent form specific to the genetic analyses will be signed by each patient prior to all sampling.

8.1.4. Data collected in the individual case report form for each patient included (Appendix 3)

A) Data relating to the physician

- Surname, first name
- Gender
- Age
- Zip code, Town
- Public or private practice
- Type of contract

B) Screening form (only for cases)

- Visit screening date
- Consentment sign date
- Inclusion and non inclusion criteria
- Demographic data: month and year of birth (MM/AAAA)
- Data relating to the initial treatment of the patient: date of diagnosis of the initial renal cancer, date of diagnosis of renal cell carcinoma
- Data relating to the status of the patient in complete remission: Sunitinib start date, number and localization of metastatic sites at initiation of Sunitinib
- Blood samples during the screening visit: yes / no sampling and date of collection. If the samples are not available during the screening visit, a period of 6 weeks between screening and sampling will be allowed.
- Histological samples: date of sampling, type of sample, method of fixation.

C) Data collected at inclusion

For the cases

- Demographic data: age, gender, height, weight
- Data on the diagnosis of patients with metastatic renal cancer in complete remission: date of initial diagnosis of kidney cancer, date of diagnosis of metastatic renal cell carcinoma, nephrectomy (Yes / No), date of nephrectomy, type of nephrectomy; fixation method, OMS pathological classification, TNM classification 2009, Furhman nuclear grade, presence of necrosis, tumor size, presence or absence of a sarcomatoid embolus component
- Data relating to the state of the patient in CR at initiation of Sunitinib: initiation date, location of metastases, number of metastatic sites, prognostic classification MSKCC

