8.2.3. Inclusion criteria

- Adult patients (≥ 18 years)
- Patients with mRCC confirmed by histological analysis
- Treated with Sunitinib according to a regimen in the text of the SmPC
- Presenting a complete remission in the preceding 5 years (according to RECIST v1.1) with Sunitinib only or combined with localized treatment (surgery, radiotherapy, cryoablation or radiofrequency ablation)
- Patients of childbearing age using a mandatory method of contraception
- Affiliated to a social security scheme
- Informed about the study methods and having given their consent

Exclusion criteria

- Complete remission occurring in the absence of treatment with Sunitinib

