2.3 Methodology of the study

[figure not shown]
This is a prospective, multi-centre, comparative, cross-sectional then observational, case-control study including 40 mRCC patients with CR when taking Sunitinib (Cases) and 80 mRCC non-CR patients treated with Sunitinib as first-line therapy (Controls).

The active participation of 15-20 oncologists means that the conditions for statistical accuracy are sufficient to meet the objectives of the study.

Each doctor will include patients with metastatic renal cell carcinoma in CR with Sunitinib (Cases) in the study.

The teams of [name] (PPD), [name] (PPD), [name] (PPD), [name] (PPD) and [name] (PPD) will include 80 patients with metastatic renal cell carcinoma without CR, at the initiation of Sunitinib, i.e. the control population. Given the rarity of the observed CR event (1.7%), it is believed that none of the patients in the control arm (N=80) will achieve a CR with Sunitinib. If any of the 80 controls achieve a CR with Sunitinib during the follow-up, they will be switched to the Case group.

These patients will be seen in consultation and should meet the inclusion and exclusion criteria.

Information will be collected via the documents listed below throughout the study.

Data relating to the doctor

- First name, Last name:
- Sex:
- Age:
- Postcode, Town;
- Type of practice;
- Sector of approval.

Screening visit (for cases only)

- Date of screening visit;
- Date of signing the consent form;
- Inclusion and exclusion criteria;
- Demographic data: month and year of birth;
- Data on the diagnosis of the mRCC patient in CR: date of initial diagnosis of kidney cancer, date of diagnosis of metastatic renal cell carcinoma;
- Data on the condition of the patient in CR at initiation of Sunitinib: date of Sunitinib initiation, location of metastases, number of metastatic sites;
- CR data: date of achieving CR, method of achieving CR, radiological evaluation of CR using Response Evaluation Criteria In Solid Tumours (RECIST);
- Blood samples taken during the screening visit: sample (Yes/No) and date of sample. If samples are not available at the screening visit, a period of 6 weeks between screening and sampling will be allowed;
- Histology samples: sample (Yes/No), date of sample, type of sample, fixing method.

Data collected at inclusion

For Cases

- Data on the inclusion and demographic data: date of signing the consent form, date of consultation, birth year, age, sex, height, weight;

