3.2 Population of patients included

The patient population included will comprise patients who have signed their consent form and have completed the inclusion visit:

- The Case population will include patients with mRCC in CR (validated after the scan review) taking Sunitinib.
- The Control population will include non-CR patients with mRCC treated with first-line Sunitinib.

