6.3.2 Other characteristics

Study population: Population of patients included

The demographic characteristics of the patients will be described by group and compared:

- Time of diagnosis of metastatic renal cell carcinoma;
- Nephrectomy (Yes/ No)*;
If Nephrectomy:
 - Extended or partial;
 - With or without adrenalectomy;
 - With or without curettage;
 - Open or laparoscopic approach;
 - Time between diagnosis of metastatic renal cell carcinoma to nephrectomy (in months);

- Pathological classification (Clear cell carcinoma / Papillary carcinoma / Chromophobe carcinoma / Bellini duct carcinoma / Medullary carcinoma / Sarcomatoid carcinoma / Other);
A list of other classifications will be presented.
- TNM classification (T / N / M and TNM);
- Tumour size (mm);
- Furhamn nuclear grade (I / II / III / IV);
- Necrosis (Yes/ No)*;
- Pulmonary embolism (Yes/No)*;
- Sarcomatoid component (Yes/No)*.

** For these qualitative variables, the odds ratio (Case versus Control) will be presented.*

The demographic characteristics of the patients, at initiation of Sunitinib, will be described by group and compared:

- Time between diagnosis of metastatic renal cell carcinoma and initiation of Sunitinib (in months);
- Location of metastases:
 - Lung (Yes/ No);
 - Bones (Yes/No);
 - Liver (Yes/ No);
 - Adrenal glands (Yes/No);
 - Pancreas (Yes/No);
 - Brain (Yes/No);
 - Lymph nodes (Yes/No);
If Lymph nodes:
 - Supra-diaphragmatic (Yes/No);
 - Sub-diaphragmatic (Yes/No);
 - Recurrence at nephrectomy site (Yes/No) ;
 - Other (Yes/ No);
A list of the other locations will be presented.
- Number of metastatic sites;
- MSKCC prognostic classification (Good prognosis/Intermediate prognosis/Poor prognosis).

The characteristics of the patients in CR will be described for the Cases:

- Time between Sunitinib initiation and CR (years);
- Method of achieving the CR (Medical treatment alone/Combined with local treatment);
If combined:
 - Surgery (Yes/No);
 - Radiotherapy (Yes/ No);
 - Radiofrequency (Yes/ No);
 - Cryoablation (Yes/ No);
 - Metastasectomy (Yes/ No);
 - Other (Yes/ No);

A list will be presented of local treatments including dates of treatment, time between the diagnosis of metastatic renal cell carcinoma and local treatment and sites exposed.

- Radiological assessment of the CR:
 - Disappearance of all known target lesions (Yes/No);
 - Disappearance of all non-target lesions (Yes/No);
 - No new lesions (Yes/No);

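### Cases are recruited up to 5 years after CR and Controls at Sunitinib start, so the primary comparison mixes factors for reaching CR with factors for still being recruitable after it

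*SAP*

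**What the plan says.** The aim in SAP 2.2.1 is "to identify factors associated with the occurrence of CR", that is, factors for an event.

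**Cases.** Protocol 3.2.2 admits patients "Presenting a complete remission in the preceding 5 years (according to RECIST v1.1"). They must also be "Informed about the study methods and having given their consent" (Protocol 8.2.3), and the consent form "will be signed by each patient before any data collection" (Protocol 8.1.3). Two scans are reviewed centrally before inclusion. SAP 3.2 defines the group thus: "The Case population will include patients with mRCC in CR (validated after the scan review) taking Sunitinib".

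**Controls.** The recruiting teams "will include 80 patients with metastatic renal cell carcinoma without CR, at the initiation of Sunitinib, i.e. the control population" (SAP 2.3). Under Protocol 8.2.4 they must be Sunitinib-naive, have a life expectancy of at least 3 months, meet haematological and liver limits (including hemoglobin above 9 g/dl), and have had no systemic treatment. The Case criteria contain none of these conditions.

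**Analysis.** SAP 4.1 plans unadjusted two-group tests. SAP 6.3.2 states: "The demographic characteristics of the patients, at initiation of Sunitinib, will be described by group and compared". The variables include metastatic sites and their number, and MSKCC class. SAP 5.2 derives Sunitinib-to-CR and CR-to-progression times, but not CR-to-screening time. No analysis by time since CR is planned, and no limitation on this point is stated.

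**The concern.** Someone who reached CR and died before being approached can never become a Case. The 40 Cases are thus a sample of patients who reached CR and remained available, not of all who reached it. Controls are sampled at the start of treatment and pass no comparable filter after treatment.

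Recording characteristics as at Sunitinib start in both groups aligns when they are measured. It does not change who survived to be counted. If a characteristic is related to survival or lasting remission after CR, it will differ between the groups even if it has no bearing on reaching CR. MSKCC class is a prognostic classification, and Protocol Appendix 8 lists number of metastatic sites as a prognostic factor, so both are plausible candidates. What is at stake is whether a reported factor can be read as a factor for the occurrence of CR.

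**Working it through.** **1. The plan's own figure.** SAP 2.5 states 80% power with 40 Cases and 80 Controls for d = 0.55. At two-sided 5% the noncentral t gives 80.4% and the normal approximation 81.1%. Converting each tabulated odds ratio to a Case frequency gives 79.8% to 84.7% (pooled z). The sample size reproduces and is not at fault. That power is for differences between the groups as sampled, whatever their cause.

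**2. The selection formula.** For a binary factor, let S1 and S0 be the probabilities that a CR patient with and without the factor is still recruitable. Let C1 and C0 be the probabilities that a patient starting Sunitinib, with and without the factor, meets the Control-only criteria. Then

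observed OR = OR for CR × (S1/S0) ÷ (C1/C0).

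The documents give none of the four probabilities.

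**3. Case selection alone (C1 = C0, true OR = 1, values assumed).** The last column is the exact chance of p < 0.05 by chi-squared test at 40/80, with control frequency 30% to 70%.

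| S1 / S0 | Observed OR | Chance of p < 0.05 |
|---|---|---|
| equal | 1.00 | about 5% |
| 0.95 / 0.80 | 1.19 | about 7% |
| 0.85 / 0.60 | 1.42 | about 12% to 14% |

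A ratio of 2.0 (0.90/0.45) would give 40% to 42% at control frequencies of 30% to 50%, but nothing in the documents supports a ratio that large.

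**4. Control selection can offset it.** If the Control-only criteria also retained 95% of patients with a favourable factor and 80% of those without, C1/C0 = 1.19 and the observed OR would be 1.19/1.19 = 1. A larger C1/C0 would push it below 1.

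**5. Effect of the recruitment window.** Assume CR dates uniform over a window of L years and exponential time in the recruitable state. Then S = (1 − e^(−hL))/(hL), with h = ln 2/median. For medians of 10 and 3 years:

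- L = 5: 0.845/0.593 = 1.43
- L = 2: 0.934/0.801 = 1.17

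Across median pairs of 10 v 5, 10 v 3, 6 v 3 and 6 v 2 years, the spurious OR is 1.17 to 1.60 for 5 years and 1.07 to 1.24 for 2 years. A shorter window reduces the bias but leaves some of it.

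**6. Can a 2-year subset serve as a test?** In the 10 v 3 scenario the log-OR shifts by ln(1.43/1.17) = 0.20. Suppose 20 of the 40 Cases fall within 2 years (assumed), with factor frequency 40%. The subset estimate then differs from the full one by chance with SD √[1/(20 × 0.24) − 1/(40 × 0.24)] = 0.32. The noise exceeds the signal.

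**7. Cases who started as Controls.** Controls who reach CR move to the Case group. At the SAP's 1.7% the expected number is 80 × 0.017 = 1.4, so nearly all 40 Cases would be prevalent.

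**The case against.** Four points carry weight.

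- **Direction.** A reader might infer that favourable prognostic features will be inflated and that Controls are unaffected. The documents do not support this. The life-expectancy, laboratory and no-prior-systemic-treatment criteria apply to Controls only, and hemoglobin is among the prognostic factors in Protocol Appendix 8. These limits may remove poor-prognosis patients from the Controls alone, which works the other way (step 4). This stands.
- **Mechanism.** Nothing in the documents shows that a given factor shortens life after CR, and SAP 2.1 reports that restarting targeted therapy after recurrence worked in most cases. If S1 = S0 there is no Case-side bias. This stands as a limit on size; it does not show that S1 and S0 are equal.
- **Scale.** The smallest harmful-direction odds ratio in the power table is 3.12, well above 1.19 or 1.42, and the excess of false positives at those values is modest. This stands. The estimates and intervals are still affected.
- **Reporting.** With complete dates, the mean CR-to-inclusion time can be recovered by subtracting the diagnosis-to-Sunitinib and Sunitinib-to-CR means from the diagnosis-to-inclusion mean. The distribution cannot, and no subset can be formed from means.

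The 5-year window was a documented feasibility decision for a rare event (Protocol section 4, Amendment 3), and this point does not ask to reverse it.

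A second tempting inference is that Cases must still be in remission when screened. Protocol 8.1.1 describes Case blood sampling as "done at screening visit during CR and during disease progression", and SAP 3.2 speaks of patients in CR. The 5-year criterion does not strictly require ongoing remission, so selection on continued CR is likely but not certain.

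**Conclusion.** The concern holds in a limited form. Cases are prevalent, Controls enter at treatment start, and the SAP neither shows nor allows for the difference. The primary comparison therefore estimates the association with CR multiplied by a recruitability ratio, and also reflects eligibility limits that only Controls had to meet.

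The size is unknown. The figures of 1.19 and 1.42 rest on assumed probabilities, on a true odds ratio of 1, and on no offset from the Control criteria. The net direction is not established. The documents support neither a prediction that particular factors will be falsely reported as determinants of CR nor a claim of a large false-positive rate. They do support changing what the primary comparison is said to show. This is an inexpensive improvement to the SAP; the sample size and the design need not change.

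**What to change.** 1. In SAP 5.2, derive time from CR to screening for Cases. In SAP 6.3.2, tabulate it (n, median, quartiles, range).
2. Pre-specify a supportive sensitivity analysis that repeats the comparisons of pre-Sunitinib characteristics using only Cases screened within 2 years of CR, against all Controls. Two years is the eligibility window that applied before Amendment 3. Show estimates and 95% CIs beside the full-sample results. Set no pass/fail rule: step 6 shows that a gate would demote real factors by chance.
3. Word the primary conclusion as factors associated with CR among patients alive and recruitable after CR.
4. State as limitations the survivor selection of Cases and the eligibility criteria that apply to Controls only.

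The cost is a few SAP lines and a small set of tables. The CR date and the screening date are already on the Case screening form (Protocol Appendix 5), so no new data are needed. The downside is that the subset will be small and imprecise, and that it reduces the Case-side bias without removing it, since those Cases also had to be alive and consenting. It does nothing about the Control-only criteria, which is why these need stating.

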2.2.2 Secondary objective(s)

The secondary objectives are to:

- Describe the therapeutic management (discontinuation or continuation of systemic treatment in CR patients);
- Search for and describe various biomarkers in a histological sample bank when initiating Sunitinib in CR patients (Cases) and non-CR patients taking Sunitinib (Controls);
- Search for and describe various biomarkers in a histology specimen bank for CR patients with Sunitinib (Cases) and at the time of recurrence, if any;
- Compare the identified biomarkers of CR patients (Cases) with those of non-CR patients taking Sunitinib during the 36 months of the study (Controls).

2.3 Methodology of the study

[figure not shown]
This is a prospective, multi-centre, comparative, cross-sectional then observational, case-control study including 40 mRCC patients with CR when taking Sunitinib (Cases) and 80 mRCC non-CR patients treated with Sunitinib as first-line therapy (Controls).

The active participation of 15-20 oncologists means that the conditions for statistical accuracy are sufficient to meet the objectives of the study.

Each doctor will include patients with metastatic renal cell carcinoma in CR with Sunitinib (Cases) in the study.

The teams of [name] (PPD), [name] (PPD), [name] (PPD), [name] (PPD) and [name] (PPD) will include 80 patients with metastatic renal cell carcinoma without CR, at the initiation of Sunitinib, i.e. the control population. Given the rarity of the observed CR event (1.7%), it is believed that none of the patients in the control arm (N=80) will achieve a CR with Sunitinib. If any of the 80 controls achieve a CR with Sunitinib during the follow-up, they will be switched to the Case group.

These patients will be seen in consultation and should meet the inclusion and exclusion criteria.

Information will be collected via the documents listed below throughout the study.

Data relating to the doctor

- First name, Last name:
- Sex:
- Age:
- Postcode, Town;
- Type of practice;
- Sector of approval.

Screening visit (for cases only)

- Date of screening visit;
- Date of signing the consent form;
- Inclusion and exclusion criteria;
- Demographic data: month and year of birth;
- Data on the diagnosis of the mRCC patient in CR: date of initial diagnosis of kidney cancer, date of diagnosis of metastatic renal cell carcinoma;
- Data on the condition of the patient in CR at initiation of Sunitinib: date of Sunitinib initiation, location of metastases, number of metastatic sites;
- CR data: date of achieving CR, method of achieving CR, radiological evaluation of CR using Response Evaluation Criteria In Solid Tumours (RECIST);
- Blood samples taken during the screening visit: sample (Yes/No) and date of sample. If samples are not available at the screening visit, a period of 6 weeks between screening and sampling will be allowed;
- Histology samples: sample (Yes/No), date of sample, type of sample, fixing method.

Data collected at inclusion

For Cases

- Data on the inclusion and demographic data: date of signing the consent form, date of consultation, birth year, age, sex, height, weight;
- Data on the diagnosis of the mRCC patient in CR: date of initial diagnosis of kidney cancer, date of diagnosis of metastatic renal cell carcinoma, nephrectomy, date and type of nephrectomy, World Health Organisation (WHO) pathological classification, TNM classification, tumour size, Furhman nuclear grade, necrosis, vascular embolism, sarcomatoid component;
- Data on the condition of the patient in CR at initiation of Sunitinib: date of initiation, location of metastases, number of metastatic sites; Memorial Sloan-Kettering Cancer Center (MSKCC) prognostic classification;
- CR data: date of achieving CR, method of achieving CR, radiological evaluation of CR using Response Evaluation Criteria in Solid Tumours after the CR.

For Controls

- Data on the inclusion and demographic data: date of signing the consent form, date of consultation, month and year of birth, age, sex, height, weight, inclusion and exclusion criteria;
- Data on the diagnosis of the mRCC patient treated with Sunitinib: date of initial diagnosis of kidney cancer, date of diagnosis of metastatic renal cell carcinoma, date of initiation of Sunitinib, nephrectomy, date and type of nephrectomy, World Health Organisation (WHO) pathological classification, TNM classification, tumour size, Furhman nuclear grade, necrosis, vascular embolism, sarcomatoid component;
- Data on the condition of the mRCC patient before initiation of Sunitinib: blood sample (Yes/No), histology samples (Yes/No) and dates of samples, location of metastases, number of metastatic sites, MSKCC prognostic classification;

Data collected during follow-up visits

In this research, patients will be followed up for three years, according to the usual procedure for this disease (visits every 2 to 3 months in line with the expert opinion set out in the guide to long-term conditions of the French National Health Authority (HAS)).

For Cases

At the visit diagnosing disease progression:

- Date of visit;
- Duration of additional Sunitinib treatment (pseudo-adjuvant), starting at CR;
- Date of progression, type of progression (local or distant);
- Metastatic sites: location and number of metastatic sites;
- Blood sample and collection date;
- Treatment administered after progression (systemic/surgical).

At the annual follow-up visit:

- Date of visit;
- Status of the disease (change);
- Changes in treatment regimen (temporary or permanent discontinuation).

At the end-of-research visit (36 months after the inclusion visit):

- Visit (Yes/ No);
- Date of visit;
- Best response to treatment received post-progression;
- Duration of administration after progression with first-line Sunitinib;
- Last news: premature discontinuation of study, date of last news, persistent CR since inclusion visit, CR after treatment of post-CR progression, disease progression, number of subsequent lines after progression, post CR;
- Death (Yes/No), date of death.

For Controls

At the 6-month and 12-month follow-up visits of Sunitinib treatment:

- Date of visit;
- Clinical assessment using RECIST criteria (response to treatment, if progression: date of progression, progression at a known metastatic site or at a new site);
- Metastatic sites: location and number of metastatic sites;
- Blood sample and collection date.

If progression:

- Date of visit;
- Date of progression, type of progression (local or distant);
- Metastatic sites: location and number of metastatic sites;
- Blood sample and collection date

At the end-of-research visit (36 months after the inclusion visit):

- Visit (Yes/ No);
- Date of visit;
- Patient still treated with Sunitinib, if yes: response to treatment, if no: progression, new treatment, date of Sunitinib discontinuation;
- Number of subsequent treatment lines;
- Last news: study stopped prematurely, date of last news;
- Death (Yes/No), date of death.

Centralised review of Computerised Tomography Scan (CT Scan) - only for patients in CR

In this research, two of the scans of CR patients (Cases) will be reviewed centrally.

- The scan at initiation of first-line Sunitinib;
- The scan showing CR.

This review will take place between the screening visit and the inclusion visit of the patient. Thus a patient can only be included after the scans have been reviewed to validate the CR.

